8.5.2. Urine for Metformin Analysis

Urine samples will be collected at times specified in the Table 1 and Table 2. Each subject will empty his or her bladder just prior to dosing. All urine voids must be collected in appropriate urine collection containers. Each collection interval should have its own collection container(s). At the end of the urine collection interval, the total volume will be measured and recorded. The urine will then be mixed thoroughly and a 5 mL aliquot will be collected for measurement of metformin PK.

The actual date and time (24-hour clock time) of each sample will be recorded. The actual times may change, but the number of samples will remain the same. All efforts will be made to obtain the samples at the exact nominal time relative to dosing.

Further detail instructions for the collection, handling, aliquoting, storage, and shipping of PK plasma and urine samples will be provided in the laboratory manual or by the sponsor.

Samples collected for measurement of plasma and urine concentrations of metformin will be analyzed using a validated analytical method in compliance with applicable standard operating procedures (SOPs).

The PK samples must be processed and shipped as indicated in the instructions provided to the investigator site to maintain sample integrity. Any deviations from the PK sample handling procedure (eg, sample collection and processing steps, interim storage or shipping conditions), including any actions taken, must be documented and reported to the sponsor. On a case-by-case basis, the sponsor may make a determination as to whether sample integrity has been compromised.

The plasma and urine samples may be used for exploratory analysis and/or evaluation of the bioanalytical method. These data will be used for internal exploratory purposes and will not be included in the clinical study report (CSR).

8.6. Pharmacodynamics

Pharmacodynamic (PD) parameters are not evaluated in this study.

8.7. Genetics

8.7.1. Specified Genetics

Genetics (specified analyses) are not evaluated in this study.

8.7.2. Banked Biospecimens for Genetics

Banked biospecimens will be collected for exploratory

pharmacogenomic/genomic/biomarker analyses and retained in the Biospecimen Banking System (BBS), which makes it possible to better understand the investigational product's mechanism of action and to seek explanations for differences in, for example, exposure, tolerability, safety, and/or efficacy not anticipated prior to the beginning of the study.

A 4-mL blood sample optimized for DNA isolation Prep D1 will be collected as local regulations and IRBs/ECs allow.

Banked biospecimens may be used for research related to drug response. Genes and other analytes (eg, proteins, ribonucleic acid (RNA), nondrug metabolites) may be studied using the banked samples.

Unless prohibited by local regulations or IRB/EC decision, participants will be asked to indicate on the consent document whether they will allow their banked biospecimens to also be used to design and conduct research in order to gain a further understanding of other diseases and to advance science, including development of other medicines for patients. This component of the sampling banking is optional for participants; they may still participate in

the study even if they do not agree to the additional research on their banked biospecimens. The optional additional research does not require the collection of any further samples.

See Appendix 5 for information regarding genetic research. Details on processes for collection and shipment of these samples can be found in the laboratory manual.

8.8. Biomarkers

8.8.1. Plasma for NMN Analysis

Blood samples of approximately 3 mL, to provide approximately 1 mL plasma, will be collected into appropriately labeled tubes containing dipotassium ethylenediaminetetraacetic acid (K_2EDTA) for measurement of plasma concentrations of NMN as specified in the Table 1 and Table 2.

The actual date and time (24-hour clock time) of each sample will be recorded. The actual times may change, but the number of samples will remain the same. All efforts will be made to obtain the samples at the exact nominal time relative to dosing. Collection of samples up to and including 10 hours after dose administration that are obtained within 10% of the nominal time (eg, within 6 minutes of a 60-minute sample) relative to dosing will not be captured as a protocol deviation, as long as the exact time of the collection is noted on the source document and data collection tool (eg, CRF/DCT). Collection of samples more than 10 hours after dose administration that are obtained ≤ 1 hour away from the nominal time relative to dosing will not be captured as a protocol deviation, as a protocol deviation, as long as the exact time of the collection of samples more than 10 hours after dose administration that are obtained ≤ 1 hour away from the nominal time relative to dosing will not be captured as a protocol deviation, as long as the exact time of the collection is noted on the source document and data collection tool (eg, CRF/DCT).

8.8.2. Urine for NMN Analysis

Urine samples will be collected at times specified in the Table 1 and Table 2. Each subject will empty his or her bladder just prior to dosing. All urine voids must be collected in appropriate urine collection containers. Each collection interval should have its own collection container(s). At the end of the urine collection interval, the total volume will be measured and recorded. The urine will then be mixed thoroughly and a 5 mL aliquot will be collected for measurement of NMN PK.

The actual date and time (24-hour clock time) of each sample will be recorded. The actual times may change, but the number of samples will remain the same. All efforts will be made to obtain the samples at the exact nominal time relative to dosing.

Further detail instructions for the collection, handling, aliquoting, storage, and shipping of PK plasma and urine samples will be provided in the laboratory manual or by the sponsor.

Samples collected for measurement of plasma and urine concentrations of NMN will be analyzed using a validated analytical method in compliance with applicable standard operating procedures (SOPs). The PK samples must be processed and shipped as indicated in the instructions provided to the investigator site to maintain sample integrity. Any deviations from the PK sample handling procedure (eg, sample collection and processing steps, interim storage or shipping conditions), including any actions taken, must be documented and reported to the sponsor. On a case-by-case basis, the sponsor may make a determination as to whether sample integrity has been compromised.

The plasma and urine samples may be used for exploratory analysis and/or evaluation of the bioanalytical method. These data will be used for internal exploratory purposes and will not be included in the clinical study report (CSR). The plasma and urine samples may be stored at a facility selected by the sponsor for a maximum of 3 years (or according to local regulations) following the last participant's last visit for the study.

8.8.3. Other Biomarkers

Leftover plasma and urine samples could be used to assess concentrations of endogenous biomarkers for OCT1, OCT2, MATE1, and/or MATE2K.

8.9. Health Economics

Health economics/medical resource utilization and health economics parameters are not evaluated in this study.

9. STATISTICAL CONSIDERATIONS

Detailed methodology for summary and statistical analyses of the data collected in this study is outlined here and further detailed in a statistical analysis plan (SAP), which will be maintained by the sponsor. The SAP may modify what is outlined in the protocol where appropriate; however, any major modifications of the primary endpoint definitions or their analyses will also be reflected in a protocol amendment.

9.1. Statistical Hypotheses

No formal inferential statistics will be applied to the safety or PK data.

9.2. Sample Size Determination

A sample size of 12 participants will provide 90% confidence intervals for the difference between treatments of ± 0.134 , ± 0.161 and ± 0.148 on the natural log scale for metformin AUC_{inf}, C_{max} and CL_r, respectively, with 80% coverage probability. The following table presents the width of 90% confidence interval for different estimated effects (Table 4):

Parameter	Estimated Effect (100*Test/Reference)	90% CI	CI Width
CLr	60%	51.73, 69.60	17.88
	70%	60.35, 81.20	20.85
	80%	68.97, 92.80	23.83
	90%	77.59, 104.40	26.81

Table 4.	Sample Size Determination
----------	---------------------------

	100%	86.21, 115.99	29.79
AUCinf	100%	87.47, 114.32	26.84
	120%	104.97, 137.18	32.22
	160%	139.96, 182.91	42.95
	200%	174.94, 228.63	53.69
Cmax	100%	85.10, 117.50	32.39
	120%	102.13, 141.00	38.88
	160%	136.17, 188.00	51.83
	200%	170.21, 235.00	64.79

Abbreviation: CI = confidence interval

These calculations are based on estimates of within participant standard deviations of 0.156, 0.188 and 0.173 for log_e AUC_{inf}, log_e C_{max} and log_e CL_r of metformin, respectively, as obtained from internal and/or external data in previous clinical studies with metformin.^{10, 11}

Participants who discontinued from the study may be replaced at the sponsor's discretion.

Population	Description
Enrolled	All participants who sign the ICD.
Randomly assigned to investigational product	Participants will be randomized to 1 of 2 treatment sequences in a 2-way crossover design. A total of 12 healthy participants will be enrolled in the study so that 6 participants will be enrolled in each treatment sequence.
PK Population	The pharmacokinetic (PK) concentration population is defined as all enrolled subjects who received at least 1 dose of metformin and in whom at least 1 plasma concentration value is reported.
Safety Population	All participants randomly assigned to investigational product and who take at least 1 dose of investigational product. Participants will be analyzed according to the product they actually received.

9.3. Populations for Analysis

9.4. Statistical Analyses

The SAP will be developed and finalized before database lock and will describe the participant populations to be included in the analyses, and procedures for accounting for missing, unused, and spurious data. This section is a summary of the planned statistical analyses of the primary and secondary endpoints.

9.4.1. Efficacy Analyses

An efficacy analysis is not applicable to this study.

9.4.2. Safety Analyses

All safety analyses will be performed on the safety population.

AEs, ECGs, BP, pulse rate, and safety laboratory data will be reviewed and summarized on an ongoing basis during the study to evaluate the safety of participants. Any clinical laboratory, ECG, BP, and pulse rate abnormalities of potential clinical concern will be described. Safety data will be presented in tabular and/or graphical format and summarized descriptively, where appropriate.

Medical history and physical examination and neurological examination information, as applicable, collected during the course of the study will be considered source data and will not be required to be reported, unless otherwise noted. However, any untoward findings identified on physical and/or neurological examinations conducted during the active collection period will be captured as AEs, if those findings meet the definition of an AE. Data collected at screening that are used for inclusion/exclusion criteria, such as laboratory data, ECGs, and vital signs, will be considered source data, and will not be required to be reported, unless otherwise noted. Demographic data collected at screening will be reported.

9.4.2.1. Electrocardiogram Analyses

Changes from baseline for the ECG parameters QT interval, heart rate, QTc interval, PR interval, and QRS complex will be summarized by treatment and time.

The number (%) of participants with maximum postdose QTc values and maximum increases from baseline in the following categories will be tabulated by treatment (Table 5):

Table 5. Safety QTc Assessment

Degree of Prolongation	Mild (msec)	Moderate (msec)	Severe (msec)
Absolute value	>450-480	>480-500	>500
Increase from baseline		30-60	>60

Abbreviation: msec = millisecond

In addition, the number of participants with uncorrected QT values >500 msec will be summarized.

9.4.3. Other Analyses

Pharmacogenomic (PGx) and endogenous biomarker PK data, other than NMN, will be collected and retained for potential future analyses, but will not be analyzed, specifically, for this study.

9.4.4. Pharmacokinetic Analyses

9.4.4.1. Analysis of Population

The PK concentration population is defined as all participants randomized and treated who have at least 1 concentration in at least 1 treatment period.

The PK parameter analysis population is defined as all participants randomized and treated who have at least 1 of the PK parameters of primary interest in at least 1 treatment period.

9.4.4.2. Derivation of Pharmacokinetic Parameters Prior to Analysis

PK parameters for metformin and NMN will be derived from the plasma concentration-time profiles and urine concentrations as shown below in Table 6.

Parameter	Definition	Method of Determination	Analyte
AUC ₂₄	Area under the plasma concentration-time profile from time zero to 24 hours	Linear/Log trapezoidal method.	N
AUC _{last}	Area under the plasma concentration-time profile from time zero to the time of the last quantifiable concentration (C_{last})	Linear/Log trapezoidal method.	N, M
AUC _{inf} ^a	Area under the plasma concentration-time profile from time zero extrapolated to infinity	$AUC_{last} + (C_{last}*/k_{el}),$ where $C_{last}*$ is the predicted plasma concentration at the last quantifiable time point estimated from the log-linear regression analysis.	Μ
C _{max} T _{max}	Maximum plasma concentration Time for C_{max}	Observed directly from data. Observed directly from data as time of first occurrence.	N, M N, M
$\mathbf{t}_{1_2}^{'}$	Terminal elimination half-life	$Log_e(2)/k_{el}$, where k_{el} is the terminal phase rate constant calculated by a linear regression of the log-linear concentration-time curve. Only those data points judged to describe the terminal log-linear decline will be used in the regression.	Μ
CL/F	Apparent clearance for extravascular dosing	Dose/AUC _{inf.}	М
V/F	Apparent volume of distribution for extravascular dosing	Apparent volume of distribution, estimated from terminal phase, for extravascular dosing.	М
Ae	Cumulative amount of drug recovered unchanged in urine	Sum of amount excreted for each collection period (Urine Concentration * Volume of Urine).	N, M
Ae%	Cumulative amount of drug recovered unchanged in urine, expressed as percent of dose	$100 \times (Ae/Dose).$	М
		Ae/AUC.	

Table 6.Derivation of PK Parameters

Actual PK sampling times will be used in the derivation of PK parameters.

PK parameters in Table 6 will be summarized descriptively by analyte and by treatment, as applicable, in accordance with Pfizer Data Standards. Concentrations will be listed and summarized descriptively by analyte, nominal PK sampling time and treatment. Individual subject and median profiles of the plasma concentration-time data will be plotted by treatment using actual and nominal times, respectively. Median profiles will be presented on both linear-linear and log-linear scales. Individual changes from baseline for metformin CL_r versus NMN CL_r will be plotted and a Pearson correlation coefficient (r) will be presented.

Natural log transformed AUC_{inf}, AUC_{last}, C_{max} and CL_r of metformin will be analyzed using a mixed effect model with sequence, period and treatment as fixed effects and participant within sequence as a random effect. Additionally, AUC₂₄, C_{max} and CL_r of NMN will also be analyzed using a mixed effect model with sequence, period and treatment as fixed effects and participant within sequence as a random effect. Estimates of the adjusted mean differences (Test-Reference) and corresponding 90% confidence intervals will be obtained from the model. The adjusted mean differences and 90% confidence intervals for the differences will be exponentiated to provide estimates of the ratio of adjusted geometric means (Test/Reference) and 90% confidence intervals for the ratios. Metformin alone will be the Reference treatment, while the metformin co-administered with PF-04965842 will be the Test treatment.

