b. Each subject will empty his or her bladder just prior to dosing. Then, all urine voids must be collected in appropriate urine collection containers. Each collection interval should have its own collection container(s). At the end of the urine collection interval, the total volume will be measured and recorded. The urine will then be mixed thoroughly. A 5 mL aliquot will be transferred to an appropriately labeled, screw capped polypropylene tube for NMN analysis. A second 5 mL aliquot will also be collected and analyzed for metformin PK concentrations.

c. PK urine collection interval for metformin concentration assessment: 0-12, 12-24, 24-36, and 36-48 hours postdose.

d. PK urine collection interval for NMN concentration assessment: 0-12 and 12-24 hours postdose.

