in normal subjects demonstrate that metformin is excreted unchanged in the urine and does not undergo hepatic metabolism (no metabolites have been identified in humans) nor biliary excretion. Renal clearance is approximately 3.5 times greater than creatinine clearance, which indicates that tubular secretion is the major route of metformin elimination. Following oral administration, approximately 90% of the absorbed drug is eliminated via the renal route within the first 24 hours, with a plasma elimination half-life of approximately 6.2 hours. In blood, the elimination half-life is approximately 17.6 hours, suggesting that the erythrocyte mass may be a compartment of distribution.^{14, 15}

Metformin will be administered following consumption of a moderate fat meal as metformin is administered with food, in standard clinical practice, to improve its tolerability. Food decreases the extent of absorption of metformin and slightly delays its absorption, as shown by an approximate 40% lower mean C_{max} , 25% lower AUC, and a 35-minute prolongation of T_{max} following administration of a single 850 mg tablet of metformin with food, compared to the same tablet strength administered fasting.^{14, 15} Administration of 4 × 100 mg PF-04965842 tablets (400 mg) with food did not change AUC_{inf}, and appeared to result in slightly lower C_{max} with reduced variability compared to fasted conditions. As such, PF-04965842 will also be administered with a moderate fat meal during co-administration with metformin and can be administered with or without food when dosed on Day 2.

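### Does the AUC in metformin renal clearance, shown without an interval, bias the primary Test/Reference ratio?

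*Protocol*

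**What the plan says.** Protocol section 9.4.4.2 (Table 6) derives CLr as Ae/AUC. The numerator is the "Sum of amount excreted for each collection period (Urine Concentration * Volume of Urine"). Footnote c to the sampling schema in section 1.3 sets its window: "PK urine collection interval for metformin concentration assessment: 0-12, 12-24, 24-36, and 36-48 hours postdose". The last plasma sample in the same schema is also at 48 h.

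Table 6 offers two metformin AUCs. AUClast is the "Area under the plasma concentration-time profile from time zero to the time of the last quantifiable concentration". AUCinf is the "Area under the plasma concentration-time profile from time zero extrapolated to infinity". SAP Table 2 adds AUC24 for metformin as a descriptive item only. The SAP repeats no CLr formula and marks CLr as calculated if data permit. For NMN the schedule is "PK urine collection interval for NMN concentration assessment: 0-12 and 12-24 hours postdose", which fits the derived AUC24.

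The CLr row of Table 6 is incomplete in the public text. The cells that name the parameter, define it and assign the analyte cannot be read, nor can the wording of footnote a. Other rows state their interval in the definition cell, so the text does not show that the interval is absent from the plan.

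**The concern.** CLr is the only primary endpoint, and a renal clearance is meaningful only if amount excreted and plasma exposure cover the same time. Here the numerator runs to 48 h. AUClast stops at the last quantifiable sample (tlast), and 48 h is nearly eight half-lives after dosing (48/6.2 = 7.7), so that sample might be below the limit of quantification. AUCinf runs past 48 h.

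If PF-04965842 slowed metformin elimination, tlast could move later under Treatment B. The Test AUClast would then cover more of the curve than the Reference one, and the fall in CLr would be exaggerated. That error is systematic, so the confidence interval would not show it.

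**Working it through.** **Inputs from the documents.** N = 12, within-participant log SD 0.173 for CLr, and stated half-width 0.148 (protocol 9.2). Metformin is eliminated "with a plasma elimination half-life of approximately 6.2 hours"; fasted Tmax is about 3 h and food delays it by 35 minutes (protocol 4.3).

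**Assumptions.** One-compartment oral kinetics; fed Tmax 3.6 h, with the absorption rate ka also varied from 0.3 to 1.0 per h; elimination wholly renal, so Test half-life = 6.2/(true CLr ratio). The limit of quantification (LLOQ) is not given and is treated as a range.

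**1. The plan's own figure.** Half-width = t(0.95, 10) × SD × √(2/12) × √(χ²(0.80, 10)/10) = 1.812 × 0.173 × 0.408 × √1.344 = 0.148. It reproduces.

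**2. Partial AUCs.** k = ln 2/6.2 = 0.112 per h; Tmax 3.6 h gives ka = 0.559 per h. AUC(0-T) is proportional to ka/(ka − k) × [(1 − e^(−kT))/k − (1 − e^(−ka·T))/ka]. As a share of AUCinf this is 91.5% to 24 h, 97.8% to 36 h and 99.4% to 48 h.

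**3. Bias factors.** Because Ae(0-48) = CLr × AUC(0-48), calculated CLr/true CLr = AUC(0-48)/AUC(used). Within Reference that is 1.087 for a 24 h AUC, 1.017 for 36 h and 0.994 for AUCinf. The Test factor divided by the Reference factor gives the bias in the ratio (1.000 = none; range over ka 0.3-1.0):

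| AUC used, Test / Reference | True ratio 1.00 | 0.90 | 0.80 | 0.60 |
|---|---|---|---|---|
| 48 h / 48 h | 1.000 | 1.000 | 1.000 | 1.000 |
| AUCinf / AUCinf | 1.000 | 0.995-0.996 | 0.988-0.990 | 0.956-0.962 |
| 36 h / 36 h | 1.000 | 1.006-1.008 | 1.015-1.018 | 1.043-1.049 |
| 24 h / 24 h | 1.000 | 1.021-1.025 | 1.049-1.056 | 1.130-1.147 |
| 48 h / 36 h | 0.979-0.985 | same | same | same |
| 36 h / 24 h | 0.918-0.942 | 0.925-0.948 | 0.934-0.956 | 0.963-0.982 |
| 48 h / 24 h | 0.898-0.928 | same | same | same |

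At ka = 0.559 per h, the 36 h / 24 h case with no true effect is 1.0169/1.0870 = 0.935, or -6.5%.

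**4. How likely the bad rows are.** The model puts the 36 h concentration at 3.3% of Cmax and the 48 h concentration at 0.9%. A Reference tlast of 24 h therefore needs an LLOQ above about 3% of Cmax, and the full -6.5% needs every participant to stop at 24 h on Reference and 36 h on Test. With no true effect, nothing would cause that shift.

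Letting an LLOQ of 0.5-5% of Cmax determine tlast, with assumed variances, gives an AUClast bias of 0% with no true effect, at most about -0.8% at a true ratio of 0.90 and -1.8% at 0.80. One such set (log SD 0.2 for elimination rate, 0.3 for absorption rate, 0.25 for exposure between participants, 0.15 between periods and 0.10 per sample) gives maxima of -0.7%, -1.7% and, at a true ratio of 0.60, -4.6%.

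**5. Scale.** -1.8% is 0.018 on the log scale; 0.018/0.148 is about one eighth of the planned half-width.

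**The case for a change.** The best case for a change is that a sole primary endpoint should leave nothing to choose. The study is sponsor-open and allows data reviews during conduct (SAP section 3), so a denominator could be picked after seeing results. SAP 5.6 lets the pharmacokineticist drop individual concentrations, which could move tlast in one period only, and SAP section 7 has no rule for an incomplete urine collection. In the extreme 48 h / 24 h case the bias is about 0.083 on the log scale (ln 0.920, at ka = 0.559 per h), more than half of 0.148. The same unlabelled formula serves NMN, for which Table 6 also lists AUClast.

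Some of this stands. The interval cannot be read from the text, and a sentence naming it would be harmless. But choosing between AUClast and AUCinf moves the result by only 1-2% at true ratios of 0.80 or higher, so there is little to gain from a late choice. The large figures need either a near-universal shift in tlast or a 24 h AUC set against 48 h urine; no analyst would call that quotient a renal clearance. Dropped samples and lost urine are handled by the same matching of intervals, and SAP 7.3 sets a parameter that cannot be derived to missing. For NMN, sampling and urine both end at 24 h.

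Nor is a fall in CLr from slower elimination unrelated to the transporter: tubular secretion is the pathway under test, so a shift in tlast would exaggerate a real effect. If tlast is the same in both treatments, the bias runs the other way.

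**Conclusion.** No change is needed. What remains is a definition not legible in the public text, and analysts fill it by matching intervals; the schedule, with plasma and urine both ending at 48 h, is built for that. Even without explicit matching, the bias in the Test/Reference ratio is nil with no true effect and about 0-2% at true ratios of 0.80 or higher. It reaches about 4-5% at 0.60, where an estimate a few percent off would still show a marked reduction. The SAP states no hypotheses and no decision rules (sections 4.1 and 4.2), so no threshold is there to be crossed.

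This rests on the protocol's 6.2 h plasma half-life, simple kinetics and an assumed LLOQ of 0.5-5% of Cmax. A longer terminal half-life enlarges the extrapolated part of AUCinf (a 4% within-treatment error at 10 h), but an error equal in both treatments cancels in the ratio, and a slower decline makes the 48 h sample easier to quantify, so that AUClast matches the urine window.
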